4.6.11 Emergency breaking of treatment assignment

Not applicable

4.6.12 Study completion and post-study treatment

Study completion for an individual patient will be 16 weeks. At the end of study, patient would continue to receive treatment as per the discretion of Investigator.

4.6.13 Early study termination

The study can be terminated at any time for any reason by Novartis. Should this be necessary, the patient should be seen as soon as possible and treated for a prematurely withdrawn patient. The investigator may be informed of additional procedures to be followed in order to ensure that adequate consideration is given to the protection of the patient's interests. The investigator will be responsible for informing IRBs and/or ECs of the early termination of the trial.

5 Visit schedule and assessments

Error! Reference source not found. lists all of the assessments and indicates with an "x" when the visits are performed.

Examination	Baseline Visit 1 (Day 1)	Visit-2 (8 ± 2 weeks)	EOS Visit 3 (16 ± 2 weeks)
Informed consent	X		
Patient demographics (sex, age, etc)	X		
Relevant medical history	X		
Vitals	X	X	X
Physical examination*	X	X	X
Height** and weight	X	X	X
Inclusion/Exclusion criteria	X		
MMSE score	X	X	X
ADCS-ADL SIV score	X		X
Concomitant medications		X	X
Treatment for AD	X	X	X
Urine examination	X	X	X
Skin irritation assessment		X	X
Patch adhesion assessment		X	X
Adverse Events (AEs)and Serious Adverse Events (SAEs) recording	X	X	X
Compliance assessment using caregiver questionnaire		X	X
EOS			X

EOS = End of Study

X = Assessment to be recorded on CRF

*Physical examination includes examination of general appearance, skin, neck (including thyroid), eyes (excluding fundus), ears, nose, throat, lungs, heart, abdomen, back, lymph nodes, and extremities. In addition, a neurological exam consisting of cranial nerve, motor and sensory assessments as performed in routine clinical practice. It also includes recording of pulse and blood pressure as per routine clinical care.

** Height is assessed only at Visit 1

At a minimum, patients will be contacted for safety evaluations during the 30 days following the last study visit or following the last administration of study treatment), including a final contact at the 30-day point. Documentation of attempts to contact the patient should be recorded in the source documentation.

5.1 Information to be collected on screening failures

For all patients who have signed informed consent and are entered into the next epoch of the study will have all adverse events **occurring after informed consent is signed** recorded on the Adverse Event CRF.

Investigators will have the discretion to record abnormal test findings on the medical history CRF whenever in their judgment, the test abnormality occurred prior to the informed consent signature.

5.2 Patient demographics/other baseline characteristics

- Date of birth or age and gender
- Relevant Medical history

At subsequent visits throughout the observation period, the following information will be updated:

- Change in concomitant medications
- Treatment taken for AD
- Physical examination which includes examination of general appearance, skin, neck (including thyroid), eyes (excluding fundus), ears, nose, throat, lungs, heart, abdomen, back, lymph nodes, and extremities. In addition, a neurological exam consisting of cranial nerve, motor and sensory assessments as performed in routine clinical practice. It also includes recording of pulse and blood pressure as per routine clinical care
- Mini-Mental State Examination (MMSE)
- ADCS-ADL SIV score

5.3 Treatment exposure and compliance

Study drug patch administered during the course of the study will be recorded on the corresponding Dosage Administration Record CRF

Other drugs administered prior to and continuing at start of study medication will be entered on the 'Concomitant medications/significant non-drug therapies prior to the start of study' CRF.

Compliance will be assessed by the investigator and/or study personnel at each visit using information provided by the patient. This information should be captured in the source document at each visit

5.4 Efficacy

5.4.1 Efficacy assessment

Mini-Mental State Examination (MMSE):

Assessing the changes in Mini-Mental State Examination (MMSE): The MMSE is a brief, practical screening test for cognitive dysfunction (Folstein et al. 1975). The test consists of

five sections (orientation, registration, attention-calculation, recall, and language & Praxis) and results in a total possible score of 30, with higher scores indicating better function. MMSE shall be recorded at the start and at each visit as mentioned in table 5.1as a part of routine clinical practice.

ADCS-ADL SIV score*:

This is a tool to assess the ability of patients with moderate to severe dementia to perform activities of daily living. ADCS-ADL SIV score is done at start and end of visit. This includes 19 questions and total score is 54. Administration instructions and Instruction card for the rater to use when administering the scale is separately provided

*"Used with permission from the NIA Alzheimer's Disease Cooperative Study (NIA Grant AG10483)".

5.4.2 Appropriateness of efficacy assessments

MMSE and ADCS-ADL SIV score is standard assessment tool for cognitive examination

5.5 Safety

5.5.1 Physical examination

A complete physical examination will include the examination of general appearance, skin, neck (including thyroid), eyes, ears, nose, throat, lungs, heart, abdomen, back, lymph nodes, extremities, vascular and neurological. If indicated based on medical history and/or symptoms, rectal, external genitalia, breast, and pelvic exams will be performed.

Information for all physical examinations must be included in the source documentation at the study site. Significant findings that are present prior to signing informed consent must be included in the Medical History part of the CRF. Significant findings made after signing the informed consent which meet the definition of an Adverse Event must be recorded on the Adverse Event section of the CRF.

5.5.2 Dermatology examination:

The following score system will be used to assess skin irritation:

I. Dermal response:

0 = No erythema (normal skin)

1 = Erythema barely visible

2 = Mild erythema

3 = Moderate erythema

4 = Severe erythema

5 = Severe erythema with vesicles or blisters

II. Other effects:

O : Edema

P : Papules (many small, red, solid, elevated lesions, surface of reaction with granular feeling)

V : Small vesicles (< 0.5 cm) circumscribed elevations with visible fluid

B : Large blister (> 0.5 cm) circumscribed elevations with visible fluid

Pu : Pustules (inflammatory small elevations containing purulent exudate)
H : Hyperpigmentation (increase of the usual pigmentation limited to the patch test area)
W : Weeping or oozing (may be a sign of vesiculation or blistering manifested by crusting)
S : Extension of the reaction beyond patch-test site (on skin area where no test product was applied)
A : Marked reaction to adhesive patch

5.5.3 Vital signs

5.5.4 Vital signs include Body temperature, BP and pulse and respiratory rate measurements. Height and weight

Height in centimeters (cm) and body weight (to the nearest 0.1 kilogram [kg] in indoor clothing, but without shoes) will be measured.

5.5.5 Patch adhesion assessment:

For the patients randomized to the Exelon® patch treatment, patch adhesion to the skin will be evaluated by the caregiver. An estimate of the patch adherence will be provided and graded according to the patch adhesiveness score for the intervals between the scheduled outpatient visits.

Following scores should be used to capture comments relating to patch adhesion:

- 0 = 90 % adhered (essentially no lift off of the skin)
- 1 = 75% to < 90% adhered (some edges only lifting off of the skin)
- 2 = 50% to < 75% adhered (less than half of the patch lifting off the skin)
- 3 = < 50% adhered but not detached (more than half the system lifting off of the skin without falling off)
- 4 = the patch was completely detached

5.5.6 Laboratory evaluations

5.5.6.1 Urinalysis

Complete urine examination will be done at baseline, visit 2 and end of study visit.

5.5.7 Appropriateness of safety measurements

The safety assessments selected are standard for this indication/patient population.

5.6 Other assessments

5.6.1 Treatment and compliance:

Caregiver medication questionnaire: Caregiver evaluation of the medications used for AD will be assessed using the Caregiver Medication Questionnaire (CMQ). The CMQ contains 4 items, which focus on caregiver evaluation of medication administration and following schedule, and 2 global items asking about caregiver perceived compliance and satisfaction..

The CMQ questionnaire asks the caregiver to respond to the items based on the patch that the patient was taking during this study.

5.6.2 Health-related Quality of Life

Not done

5.6.3 Pharmacokinetics

Not done

5.6.4 Pharmacogenetics/pharmacogenomics

Not done

5.6.5 Other biomarkers:

Not done

6 Safety monitoring

6.1 Adverse events

An adverse event (AE) is any untoward medical occurrence (i.e., any unfavorable and unintended sign [including abnormal laboratory findings], symptom or disease) in a subject or clinical investigation subject after providing written informed consent for participation in the study. Therefore, an AE may or may not be temporally or causally associated with the use of a medicinal (investigational) product.

The occurrence of adverse events should be sought by non-directive questioning of the patient at each visit during the study. Adverse events also may be detected when they are volunteered by the patient during or between visits or through physical examination, laboratory test, or other assessments.

Abnormal laboratory values or test results constitute adverse events only if they fulfill at least one of the following criteria:

- they induce clinical signs or symptoms,
- they are considered clinically significant,
- they require therapy.

Clinically significant abnormal laboratory values or test results should be identified through a review of values outside of normal ranges/clinically notable ranges, significant changes from baseline or the previous visit, or values which are considered to be non-typical in patient with underlying disease. Investigators have the responsibility for managing the safety of individual patient and identifying adverse events. Alert ranges for labs and other test abnormalities are included in Appendix 1.

Adverse events should be recorded in the Adverse Events CRF under the signs, symptoms or diagnosis associated with them accompanied by the following information.

- the severity grade
 - mild: usually transient in nature and generally not interfering with normal activities
 - moderate: sufficiently discomforting to interfere with normal activities
 - severe: prevents normal activities
- its relationship to the study treatment (no/yes), or its duration (start and end dates) or if the event is ongoing an outcome of not recovered/not resolved should be reported.
- whether it constitutes a serious adverse event (SAE)
- action taken regarding study treatment
- whether other medication or therapies have been taken (concomitant medication/non-drug therapy)
- its outcome (not recovered/not resolved; recovered/resolved; recovering/resolving, recovered/resolved with sequelae; fatal; or unknown)

An SAE is any adverse event (appearance of (or worsening of any pre-existing) undesirable sign(s), symptom(s) or medical conditions(s) which meets any one of the following criteria

- is fatal or life-threatening
- results in persistent or significant disability/incapacity
- constitutes a congenital anomaly/birth defect
- requires inpatient hospitalization or prolongation of existing hospitalization, unless hospitalization is for
 - routine treatment or monitoring of the studied indication, not associated with any deterioration in condition
 - elective or pre-planned treatment for a pre-existing condition that is unrelated to the indication under study and has not worsened since signing the informed consent
 - treatment on an emergency outpatient basis for an event not fulfilling any of the definitions of a SAE given above and not resulting in hospital admission
 - social reasons and respite care in the absence of any deterioration in the patient's general condition
- is medically significant, i.e. defined as an event that jeopardizes the patient or may require medical or surgical intervention to prevent one of the outcomes listed above.

All malignant neoplasms will be assessed as serious under “medically significant” if other seriousness criteria are not met.

Unlike routine safety assessments, SAEs are monitored continuously and have special reporting requirements; see Section 7.2.

All adverse events should be treated appropriately. Treatment may include one or more of the following: no action taken (i.e. further observation only); [study treatment/investigational] treatment dosage adjusted/temporarily interrupted; study drug(s) permanently discontinued; concomitant medication given; non-drug therapy given. The action taken to treat the adverse event should be recorded on the Adverse Event CRF.

Once an adverse event is detected, it should be followed until its resolution or until it is judged to be permanent, and assessment should be made at each visit (or more frequently, if necessary) of any changes in severity, the suspected relationship to the study treatment, the interventions required to treat it, and the outcome.

Information about common side effects already known about the investigational drug can be found in the package insert. This information will be included in the patient informed consent and should be discussed with the patient during the study as needed.

The investigator should also instruct each patient to report any new adverse event (beyond the protocol observation period) that the patient, or the patient’s personal physician, believes might reasonably be related to study treatment. This information should be recorded in the investigator’s source documents, however, if the AE meets the criteria of an SAE, it must be reported to Novartis.

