Study design	
This is a multicenter, prospective, phase IV study evaluating safety, tolerability and effectiveness of rivastigmine 27 mg -15 cm² transdermal patch prescribed in patients with severe dementia of the Alzheimer's type as per discretion of treating physician.
 
The prescription decision shall be independent of decision for inclusion in the study. Patients treated according to local routine clinical practice will be enrolled in the study upon signing an Informed Consent. Eligibility for study entry will be determined by the study investigator, in accordance with the selection criteria below. Signing of the Informed Consent defines the study entry visit. Routine urine examination shall be done to detect any UTI. Compliance to treatment directions shall be reviewed by treating investigator at every visit.
 
After 8 week and at 16 week, it is expected for the physician to follow up as per routine practice in India. The treating physician will assess the safety, tolerability and effectiveness of the rivastigmine 27 mg -15 cm² transdermal patch and may consider continuing or changing the therapy

Population	Alzheimer's disease patients
Inclusion criteria	
1. Patients willing to participate in the study by providing written informed consent.2. Patients diagnosed with severe dementia secondary to Alzheimer's disease (AD)
Exclusion criteria	
1. Contraindication as per PI2. Patients simultaneously participating in other studies

Investigational and reference therapy	Rivastigmine patch 15cm2
Efficacy assessments	
• Mini-Mental State Examination (MMSE)• ADCS-Activities of Daily Living Inventory – Severe Impairment Version (ADCS-ADL SIV) Score
Safety assessments	
• Urine examination• Skin reaction at patch• Patch adhesion• Adverse events
Other assessments	
• Compliance by Caregiver medication questionnaire
Data analysis	The primary safety objective of this study will be assessed by collecting adverse events. The key secondary objective of this study will be assessed by compliance measured by caregiver questionnaire, skin reaction and change in MMSE from baseline
Key words	Alzheimer, Rivastigmine,

1 Introduction

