4.1 Inclusion criteria

Patients eligible for inclusion in this study have to fulfill all of the following criteria:

- Patients willing to participate in the study by providing written informed consent.
- Patients diagnosed with severe dementia secondary to Alzheimer's disease (AD)
- Patient's prescribed with rivastigmine 27mg -15 cm² transdermal patch as per discretion of treating physician

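### Protocol 6.1 names only the patient as informant for adverse events in a severe-dementia population, so the primary AE incidence is at risk of under-ascertainment

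*Protocol*

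**What the plan says.** The data analysis row of the protocol synopsis says: "The primary safety objective of this study will be assessed by collecting adverse events". SAP 9.6.1 repeats this and analyses the events in the safety population.

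Protocol 6.1 sets out how events are found. The one active method is: "The occurrence of adverse events should be sought by non-directive questioning of the patient at each visit during the study". The next sentence adds events that are "volunteered by the patient during or between visits or through physical examination, laboratory test, or other assessments". Sections 6.1 and 6.2 do not mention the caregiver, and the SAP names no informant for adverse events. The text under the visit schedule in Protocol section 5 provides for safety contacts over the 30 days after the last visit or last dose, again with patients.

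Severe dementia secondary to Alzheimer's disease is an inclusion criterion (Protocol 4.1). Visits are at Day 1, 8 ± 2 weeks and 16 ± 2 weeks.

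**The concern.** An open question about the past two months depends on the respondent's memory and ability to report. Here the only named respondent has severe dementia, and Protocol 9.2 already foresees patients who cannot give consent themselves. The person who sees the patient between visits is available, and the protocol relies on that person for other information.

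The study has no comparator (Protocol 3.4), so missed events cannot cancel between arms. They can only lower the reported incidence, which makes the drug look safer in a study that the health authority required as a condition of marketing authorisation. Some sites may ask the caregiver and others may not. Neither the AE items in Protocol 6.1 nor the planned AE listing (16.2.7.1 in the SAP catalogue) records who was asked, so that variation would be invisible in the analysis.

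**Working it through.** **Who is named as informant**

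| Information | Place | Person named |
|---|---|---|
| AE questioning at visits | Protocol 6.1 | patient |
| AEs volunteered at or between visits | Protocol 6.1 | patient |
| 30-day safety contact | Protocol 5, under the schedule | patient |
| Acting when a tolerability problem arises | Protocol 4.6.6 | caregiver |
| Patch adhesion between visits | Protocol 5.5.5 | caregiver |
| Administration, compliance, satisfaction (CMQ) | Protocol 5.6.1, Appendix 1 | caregiver |

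The CMQ has no AE item, and its questions on skipped or late patches cover only the past week.

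**Length of recall.** Visit 2 falls 6 to 10 weeks after baseline. With Visit 3 at 14 to 18 weeks, the second interval runs from 14 − 10 = 4 weeks to 18 − 6 = 12 weeks.

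**Which events are exposed.** Urine examination is scheduled at all three visits, and skin irritation scoring at Visits 2 and 3, so those findings depend less on what the patient says. Protocol 3.6 gives nausea, vomiting and diarrhoea as the most frequently reported events across the rivastigmine trials. An episode that ends weeks before a visit would not normally appear on examination or urinalysis.

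**The plan's own figure.** Inputs from Protocol 8.7: p = 0.746, maximum error 10% of p, so d = 0.0746, in 90% of cases (z = 1.645).

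n = z² p(1 − p)/d² = 1.645² × 0.746 × 0.254 / 0.0746² = 92.1, rounded up to 93. This reproduces the stated 93. Adding 10% gives 93 × 1.10 = 102.3, against the stated 102. The formula allows for sampling error only; it assumes that every affected patient is detected.

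**Illustration.** Let s be the share of patients with at least one AE who are recorded as having one. The documents give no value for s, so the values below are assumptions. Apparent incidence = s × 0.746. The last column is the exact binomial probability, with n = 93, that the observed proportion lies within 10% of 0.746.

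| s (assumed) | Apparent incidence | Loss (points) | Probability within the margin |
|---|---|---|---|
| 1.00 | 74.6% | 0 | 0.91 |
| 0.95 | 70.9% | 3.7 | 0.78 |
| 0.90 | 67.1% | 7.5 | 0.50 |
| 0.80 | 59.7% | 14.9 | 0.07 |

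**The case against.** A reader might infer that incidence *will* be under-ascertained if sites follow the protocol. The documents do not support that. The sentence in 6.1 is a recommendation, it does not exclude the caregiver, and the same section makes investigators responsible for identifying adverse events. No detection rate is given.

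Questioning is also not the only route. Section 6.1 adds examination, laboratory tests and other assessments. SAP Table 14.3.8 includes a yes/no item on the occurrence of a skin reaction to the patch, separate from the dermal score, which could pick up a reaction that has since resolved. Concomitant medications recorded at Visits 2 and 3 may point to treated events. For the ACTION study in severe disease, Protocol 1.2 names application-site erythema or dermatitis and urinary tract infection as the most frequent events, and both have scheduled assessments. A patient drops out of the numerator only if every one of that patient's events is missed. All of this stands and narrows the concern to transient events between visits.

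The illustration has limits too. A 10% loss matches the planned error only because that error is defined as 10% of p. The 74.6% is an incidence observed over 24 weeks in another study, not a known true 16-week rate, and that study may itself have missed events.

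Two other sentences look like further support but are not. Protocol 5.3 assesses compliance "using information provided by the patient", but SAP 9.6.2 analyses compliance from the caregiver-completed CMQ. The instruction "The investigator should also instruct each patient to report any new adverse event" concerns events after the observation period, which go into source documents and so do not bear on incidence within the study.

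What remains is that the only prompted enquiry, and the only volunteered report, are tied to the person least able to give them. That some sites may ask the caregiver anyway does not answer this, because the informant would then differ between sites without record.

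**Conclusion.** The point holds as a risk, not as a demonstrated loss. Protocol 6.1 names the patient alone as AE informant in a population with severe dementia and visits about 8 weeks apart. Any resulting bias in the primary incidence would be downward and would fall mainly on transient symptoms between visits; skin and urine findings are less exposed.

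Its size cannot be derived from the documents. The range of 70.9% to 59.7% rests entirely on assumed detection of 95% to 80% of affected patients, and on treating 74.6% as the true incidence. The planned sample size of 93 reproduces and is not in question. A larger sample would not remove a bias of this kind. This is a worthwhile, low-cost improvement rather than a flaw that invalidates the study.

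**What to change.** In Protocol 6.1, direct AE questioning to the patient and the caregiver, and accept volunteered reports from either. Do the same for the 30-day safety contact in Protocol section 5. Record the informant (patient, caregiver or both) with each event on the AE CRF, and show it in Listing 16.2.7.1.

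The cost is a short protocol amendment, one CRF field, and a few extra minutes at each visit with a caregiver who already completes the CMQ at both follow-up visits.

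The documents do not state enrolment status, but the CRF was final in April 2018 and the SAP is dated December 2022. If data collection is already complete, an amendment cannot repair the data. The study report should then say, from source documents where available, who was asked about adverse events, and state the likely downward direction of bias as a limitation.
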